### 2.1.3.1. Parsaclisib Pharmacokinetics

Based on an ex vivo whole blood assay, parsaclisib 20 mg QD provided exposure ranging from approximately 2-fold above the IC90 at trough to 19-fold above the IC90 at peak.

Study INCB 50465-101 was a Phase 1/2 study that examined parsaclisib monotherapy dose escalation (5-45 mg QD) and dose expansion (20 mg and 30 mg QD). In this study, the vast majority (93%) of responses occurred by the first assessment (~ 9 weeks) in participants with R/R DLBCL (n = 23), FL (n = 14), MZL (n = 9), or MCL (n = 9; data cutoff date of 18 AUG 2017). For the participants with NHL who received parsaclisib monotherapy, an objective response was achieved by 7 of 23 participants (30%) with DLBCL, 10 of 14 participants (71%) with FL, 7 of 9 participants (78%) with MZL, and 6 of 9 participants (67%) with MCL. Among the 72 participants treated with parsaclisib monotherapy, the most common ( $\geq 30\%$ ) nonhematologic TEAEs of any grade were diarrhea/colitis (36%), nausea (36%), fatigue (31%), and rash (31%). New or worsened Grade 3/4 neutropenia occurred in 19% of participants based on laboratory data. The  $t_{max}$  of parsaclisib was 0.5 to 1 hour, the terminal half-life was approximately 8.6 to 11.5 hours, and the exposure appeared to be dose-proportional between 5 mg and 45 mg QD at steady state. The PK analyses demonstrated robust and sustained pathway inhibition at all dose levels tested ([Forero-Torres et al 2019, parsaclisib IB](#)).

The continuation of parsaclisib at a daily but lower dose (2.5 mg) is expected to provide sufficient exposure (estimated to be approximately  $1 \times IC_{90}$  at peak) to maintain PI3K pathway inhibition while minimizing the frequency of late-onset AEs that may lead to study treatment withdrawal. Evaluation of this dosing regimen is ongoing in 3 Phase 2 studies in participants with FL (INCB 50465-203), MZL (INCB 50465-204), and MCL (INCB 50465-205).

Preliminary data from participants receiving this regimen suggest that continuous QD dosing has demonstrated benefit in both aggressive and indolent NHL, and the emerging safety profile is consistent with that known for parsaclisib.

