#### 2.1.5.1. Tafasitamab + Idelalisib in Relapsed/Refractory Chronic Lymphocytic Leukemia (COSMOS Study)

An open-label, multicenter, Phase 2 study (COSMOS Study, NCT02639910) was performed to evaluate the safety and preliminary clinical activity of tafasitamab combined with idelalisib or venetoclax in 2 independent cohorts of study participants with R/R CLL who were pretreated with a BTK inhibitor. Tafasitamab 12 mg/kg was administered as an IV infusion weekly for Cycles 1 to 3 (with an additional loading dose on Day 4 in Cycle 1), every other week for Cycles 4 to 6, and monthly from Cycle 7 onward (with each cycle lasting 28 days).

As of the data cutoff date of 08 OCT 2019, all 11 participants treated with tafasitamab and idelalisib were included in the safety analysis set and experienced TEAEs (244 events). Most TEAEs reported were Grade 1 or 2 severity (181/244 events). The most common TEAEs were anemia (63.6%), dyspnea (54.5%), and cough (54.5%). The most common  $\geq$  Grade 3 TEAEs were hematologic and included neutropenia (45.5%), anemia (27.3%), and thrombocytopenia (27.3%). Eight participants (72.7%) had 19 treatment-emergent SAEs. Hematologic SAEs included anemia (1 patient, Grade 3), thrombocytopenia (1 patient, Grade 3), and pancytopenia (1 patient, Grade 2). The most common nonhematologic SAE was pneumonia (2 patients,  $\geq$  Grade 3). Four participants (36.4%) had SAEs suspected to be related to tafasitamab (cardiac failure, acute pancreatitis, pneumonia, arthralgia), and 7 participants (63.6%) had SAEs suspected to be related to idelalisib (cardiac failure, pneumonia, bronchitis, septic shock, upper respiratory tract infection, acute pancreatitis, increased C-reactive protein level, pancytopenia). Tafasitamab treatment was interrupted due to TEAEs in 10 participants (90.9%), mainly due to IRRs (in 5/11 participants, 45.5%). The IRRs were Grade 2 in 4 of 5 participants and Grade 3 in 1 participant. No participants discontinued tafasitamab permanently due to IRRs. Idelalisib treatment was interrupted due to TEAEs in 9 participants (81.8%), and 5 participants (45.5%) permanently discontinued idelalisib due to TEAEs.

A best response of CR or PR was achieved in 10 of 11 participants (90.9%; CR: n = 1, PR: n = 9).

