## **5.5. Replacement of Participants**

Participants who do not experience a DLT and do not receive at least 3 doses of tafasitamab and 21 days of treatment with parsaclisib 20 mg QD will be replaced to ensure that there are 10 evaluable participants within each disease-specific cohort.

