**Table 7: Definition of Dose-Limiting Toxicity**

Toxicity	Definition
Nonhematologic	

• Any liver function abnormalities that meet the definition of Hy's lawa.

• <math>\geq</math> Grade 4 tumor lysis syndrome or Grade 3 tumor lysis syndrome requiring dialysis.

• <math>\geq</math> Grade 4 fatigue lasting for <math>\geq</math> 7 days.

• <math>\geq</math> Grade 4 IRR.

• <math>\geq</math> Grade 3 CRS.

• Any other <math>\geq</math> Grade 3 nonhematologic toxicity except nausea, vomiting, electrolyte abnormality, or liver function abnormality

Hematologic	

• <math>\geq</math> Grade 3 hematologic toxicities lasting for <math>> 3</math> days excluding neutropenia and lymphocytopenia (also excluding thrombocytopenia in Groups 3 and 5).

• Grade 4 neutropenia (<math>ANC < 0.5 \times 10^9/L</math>) lasting for <math>\geq</math> 7 days in participants with pretreatment <math>ANC > 1 \times 10^9/L</math> under appropriate use of G-CSF (if G-CSF is required to manage neutropenia, the neutropenia is considered a DLT in Cohorts 1 and 2).

• Grade <math>\geq 4</math> thrombocytopenia in Cohorts 3 and 5.

• Febrile neutropenia.

General	

• Any death not clearly due to the underlying disease or extraneous causes.

• Any toxicity other than described above that (in the opinion of the investigator) is potentially life-threatening and cannot be controlled with standard measures.

• Any other toxicity that a primary investigator and the sponsor agree on being reported as a DLT.

a Hy's law is defined as 1) ALT or AST elevation  $> 3 \times ULN$ , 2) total bilirubin  $> 2 \times ULN$  without initial findings of cholestasis (elevated serum alkaline phosphatase), and 3) no other apparent possible causes of aminotransferase elevation and hyperbilirubinemia, including but not limited to viral hepatitis, pre-existing chronic or acute liver disease, or the administration of other drug(s) known to be hepatotoxic.

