### 6.5.2. Procedures for Cohort Review

Telephone conferences will be scheduled by the sponsor with study investigators to review cohort-specific data and overall safety data, to adjudicate individual high-grade AEs as potentially dose-limiting, and guide other major study decisions.

The decision to continue enrollment into each of the malignancy subtype cohorts will be based on the frequency of DLTs in the first 10 DLT-evaluable participants and review of ongoing

safety data. After the safety review is completed and the dose confirmation decision is made, the dose expansion period for that cohort will begin, and up to 10 additional participants will be enrolled (up to a total of 20 evaluable participants in each cohort across both study periods).

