**Table 8: Guidelines for Interruption and Restarting of Study Treatment**

Adverse Event	Value or Grade	Recommendation
Grade 3/4 neutropenia judged to be related to study drugs	ANC decreases to $< 1.0 \times 10^9/L$ for at least 7 days OR ANC decreases to $< 1.0 \times 10^9/L$ with an associated body temperature $\geq 38.5^{\circ}C$ ( $101.3^{\circ}F$ ) OR ANC decreases to $< 0.5 \times 10^9/L$	Interrupt tafasitamab and parsaclisib dosing. Follow CBC every 7 days. Growth factors (eg, G-CSF) and antimicrobial prophylaxis are to be used, as per local guidelines.
	ANC returns to $\geq 1.0 \times 10^9/L$	Provided all other criteria are fulfilled, resume dosing of tafasitamab and/or parsaclisib at the same dose. Monitor as clinically indicated.
Grade 2-4 thrombocytopenia judged to be related to study drugs	Platelet count decreases to $< 75 \times 10^9/L$	Interrupt tafasitamab and parsaclisib dosing. Follow CBC every 7 days.
	Platelet count decreases to $\geq 75 \times 10^9/L$	Provided all other criteria are fulfilled, resume dosing of tafasitamab and/or parsaclisib at the same dose. Monitor as clinically indicated.
Other clinically significant toxicities judged to be related to study drugs	Grade 3	Interrupt the administration of the study drug(s) to which the toxicity is judged to be related to up to 28 days until the toxicity has resolved to $\leq$ Grade 1.
	Toxicities resolve to $\leq$ Grade 1	Restart tafasitamab and parsaclisib at the same doses. If assessed as related to parsaclisib, restart at the next lower dose of parsaclisib (see Table 11). Monitor as clinically indicated.
	Recurrent Grade 3 after 2 dose reductions of parsaclisib	Discontinue tafasitamab and parsaclisib administration and follow-up per Protocol. Exceptions require approval of sponsor.
	Grade 4	Discontinue tafasitamab and parsaclisib administration and follow-up per Protocol. Exceptions require approval of sponsor.

CBC = complete blood count.

Note: If, based on medical judgment, the treating physician considers a laboratory parameter change or AE not to be a study drug-related toxicity, but to represent a natural fluctuation in or progression of the underlying disease, then it is at the physician's discretion and assessment of the individual risk/benefit ratio to determine whether the participant should be dosed. The decision and rationale behind the decision should be documented in the source data.

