### **6.6.3. Criteria for Permanent Discontinuation of Study Drug**

The occurrence of unacceptable toxicity will require that the study drug be permanently discontinued. Unacceptable toxicity is defined as follows:

- The occurrence of an AE related to the study drug that, in the judgment of the investigator or the sponsor's medical monitor, compromises the participant's ability to continue study-specific procedures or is considered not to be in the participant's best interest.
- A persistent AE requiring a delay of study treatment for more than 14 days unless a greater delay has been approved by the sponsor.

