**Table 16: Populations for Analysis**

Population	Description
All-screened set	All participants who signed the ICF.
FAS	The FAS includes all participants who received at least 1 dose of study drug. The FAS will be used for the summary of demographics, baseline characteristics, participant disposition, and analyses of all safety and efficacy data.
DLT evaluable set	The DLT evaluable set will include all participants who received at least 3 of 4 doses of tafasitamab and 21 days of treatment with parsaclisib 20 mg QD during the first cycle (28 days) or have experienced a DLT. Participants who are considered not evaluable will be replaced.
Efficacy evaluable set	The efficacy evaluable population includes all participants enrolled in the study who have received at least 1 dose of study drug and completed a baseline scan and meet at least one of the following criteria: 

• <math>\geq 1</math> post baseline scan

• The participant has participated in the study for a minimum of 42 days

• The participant has discontinued from treatment or died prior to the first scheduled postbaseline scan

PK evaluable set	The PK evaluable population will include all participants who received at least 1 dose of study drug and provided at least 1 postdose PK plasma sample.
Immunogenicity analysis set	All participants who received at least 1 dose of study treatment and have at least 1 evaluable anti-tafasitamab antibody (ADA) assessment.

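### In Cohorts 3-5, drug-related neutropenia that is not a listed DLT can hold both drugs for more than 7 days in Cycle 1; the participant is then replaced, which biases the DLT rate down

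*Protocol*

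**What the plan says.** **What counts as a DLT.** In Protocol Section 6.5.1, Table 7, the general hematologic criterion (Grade 3 or higher for more than 3 days) excludes neutropenia in every cohort. Neutropenia has its own entries: febrile neutropenia, and Grade 4 lasting at least 7 days in participants whose pretreatment ANC was above 1 × 10^9/L. A parenthesis adds that "if G-CSF is required to manage neutropenia, the neutropenia is considered a DLT in Cohorts 1 and 2". Cohorts 3-5 have no such addition. A final entry lets an investigator and the sponsor agree to report any other toxicity as a DLT.

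**When dosing stops.** For drug-related neutropenia, Table 8 holds both drugs at ANC below 0.5 for any duration, at ANC below 1.0 for at least 7 days, or at ANC below 1.0 with fever. The instruction is: "Interrupt tafasitamab and parsaclisib dosing. Follow CBC every 7 days. Growth factors (eg, G-CSF) and antimicrobial prophylaxis are to be used". Dosing resumes when ANC reaches 1.0. Section 6.6.2 describes the table as general guidance.

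**Who is replaced.** Section 5.5 covers "Participants who do not experience a DLT and do not receive at least 3 doses of tafasitamab and 21 days of treatment" with parsaclisib, and replaces them. Table 16 says the same of the DLT evaluable set: "Participants who are considered not evaluable will be replaced". SAP Section 5.3.4 repeats the rule. None of these places makes an exception for doses missed because of drug toxicity.

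**What depends on it.** DLT incidence is part of the Phase 1b primary endpoint. Section 6.5.2 bases expansion on DLT frequency in the first 10 DLT-evaluable participants together with ongoing safety data. Under Section 6.5.3, DLTs in 2 or more participants of a cohort halt its enrollment until a nonbinding iDSMB review is complete.

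**The concern.** Table 8 stops treatment at a milder degree of neutropenia than Table 7 lists as dose-limiting. A participant can therefore lose the minimum exposure to drug toxicity without having a listed DLT. The replacement rule then treats that participant as uninformative and enrolls another. Failing to complete the minimum dosing because of the drugs is evidence against tolerability, so the missingness is not neutral: the set that remains is selected for having tolerated the drugs.

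At stake are the reported DLT rate and whether a cohort reaches the 2-DLT pause. Neutropenia is an expected toxicity here. For parsaclisib alone, Section 2.1.3.1 states: "New or worsened Grade 3/4 neutropenia occurred in 19% of participants based on laboratory data". For tafasitamab with idelalisib, Section 2.1.5.1 gives Grade 3 or higher neutropenia in 45.5% of 11 participants. Both describe treatment as a whole, not Cycle 1.

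**Working it through.** **1. The plan's own figures (Section 10.1), n = 10.** At least 1 DLT: 1 − 0.8^10 = 89.3% and 1 − 0.7^10 = 97.2%, as stated. One-sided 95% upper limits: 0/10 gives 1 − 0.05^(1/10) = 25.9%; 1/10 gives 39.4%, consistent with the stated bound of 39.5%. These are correct and not in dispute.

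**2. When a hold leads to replacement.** In Cycle 1, parsaclisib is daily on Days 1-28 and tafasitamab is due on Days 1, 8, 15 and 22. The minimum is 21 parsaclisib days and 3 infusions.

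| Days held | Parsaclisib days | Infusions | Status |
|---|---|---|---|
| 8-14 | 21 | 3 | evaluable, non-DLT |
| 8-21 | 14 | 2 | replaced |
| 15-21 | 21 | 3 | evaluable, non-DLT |
| 15-28 | 14 | 2 | replaced |
| 22-28 | 21 | 3 | evaluable, non-DLT |

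In general, a hold of 7 days or less costs at most 7 parsaclisib days and one infusion, so the participant stays evaluable. A hold of 8 or more days starting on Days 2-21 leaves at most 20 parsaclisib days, so the participant is replaced. A hold from Day 22 onward can cost at most 7 days of the cycle.

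**3. An example that follows the text.** Cohort 3, no fever, ANC 0.8 at the weekly counts on Days 8, 15 and 22. By Day 15 the count has been below 1.0 for 7 days, so Table 8 holds both drugs. Day 22 does not permit a restart, and the next weekly count is Day 29. Exposure is 14 parsaclisib days and 2 infusions. The event never reached Grade 4, so it is not a listed DLT, and the participant is replaced. If ANC is still below 1.0 on Day 29, the delay passes 14 days. Section 6.6.3 includes in unacceptable toxicity "A persistent AE requiring a delay of study treatment for more than 14 days" and requires permanent discontinuation unless the sponsor approves a longer delay.

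**4. Effect on the 2-DLT trigger.** Let p be the rate of other DLTs and q the share of participants with unlisted neutropenia who fall below the minimum exposure. The documents give neither. Treat the two as mutually exclusive.

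- Replaced: DLT rate in the evaluable set r = p/(1 − q).
- Counted as DLTs: r = p + q.
- P(2 or more in 10) = 1 − (1 − r)^10 − 10r(1 − r)^9.

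With p = 10%:

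| q | r, replaced | P(≥ 2) | r, counted | P(≥ 2) |
|---|---|---|---|---|
| 0% | 10.0% | 26% | 10% | 26% |
| 2% | 10.2% | 27% | 12% | 34% |
| 5% | 10.5% | 28% | 15% | 46% |
| 10% | 11.1% | 31% | 20% | 62% |

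For scale only, q of 2%, 5% and 10% is about a tenth, a quarter and half of 19%. The other assumption also matters. At q = 5%, the pair (replaced, counted) is 9% and 26% for p = 5%, and 66% and 76% for p = 20%.

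**The case against.** **Excluding neutropenia looks deliberate.** Section 6.6.2 notes that participants may enter with extensive pretreatment or marrow infiltration. That is a fair reason not to call every Grade 3 count a DLT. It does not explain why someone who missed the minimum exposure because of the drugs should leave the denominator.

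**There are safeguards.** Section 6.5.2 provides calls "to adjudicate individual high-grade AEs as potentially dose-limiting". Table 7 has the catch-all by agreement. The events remain among the TEAEs in the FAS, TEAE incidence and severity is itself a primary endpoint, and the iDSMB sees overall safety data. All of this stands, and it lowers the harm. But each route is discretionary, and no text says that toxicity-caused non-evaluability should be counted. The iDSMB charter is not among the documents.

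**Table 8 is guidance.** A new DLT entry would depend on holding decisions that are partly discretionary. That is true, but the existing exposure minimum already depends on the same decisions.

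**The logic is not specific to neutropenia.** This is also fair, and the fallback under the fix therefore covers any study-drug-related toxicity.

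**Stronger readings that the documents do not support:**

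- A reader might infer that any unlisted dose-stopping neutropenia leads to replacement. It does not; shorter or later holds leave an evaluable non-DLT.
- A reader might take ANC below 0.5 on Day 8 and 0.7 on Day 15 as Grade 4 for under 7 days. Weekly counts cannot show that, and a Grade 4 record from Day 8 to Day 15 arguably meets the 7-day criterion. The Grade 4 route to replacement needs an extra count showing earlier improvement, followed by ANC between 0.5 and 1.0 long enough for the hold to pass 7 days.
- A reader might extend the gap to Cohorts 1 and 2. There the result turns on the G-CSF parenthesis, which does not say which of the entry's other conditions still apply or what makes G-CSF required. That is missing detail, and this point does not rest on it.

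**Conclusion.** The point holds for Cohorts 3-5, and only for holds that start before Day 22 and last more than 7 days. Within that scope the rules as written remove an adverse tolerability outcome from the DLT numerator and its participant from the evaluable set. The bias runs in one direction, towards a lower DLT rate.

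Its size cannot be determined. The 19% and 45.5% are whole-treatment figures, the second from 11 CLL participants on a different PI3Kδ inhibitor. Neither is limited to Cycle 1, to afebrile or unlisted events, or to holds beyond 7 days. The contrast of 27% to 31% with 34% to 62% is an illustration under assumed rates (p = 10%, q from 2% to 10%, with q restricted to participants actually replaced). It should not be read as a forecast, and it vanishes at q = 0.

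The consequence is an understated DLT rate and possibly a missed pause for a nonbinding review. A reader might infer that the toxicity would go unseen; the FAS safety reporting rules that out. This is an optional improvement, worth making because it costs little.

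**What to change.** Add one entry to Table 7 for all cohorts: *study-drug-related neutropenia because of which a participant receives fewer than 3 of 4 tafasitamab doses or fewer than 21 days of parsaclisib in Cycle 1*. Section 5.5, Table 16 and SAP Section 5.3.4 already keep anyone with a DLT, so they need no change, and no existing criterion is narrowed.

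If the sponsor does not want this to be a DLT, report to the iDSMB, by cohort and alongside the DLT count, how many participants were non-evaluable because of study-drug-related toxicity, and show the DLT rate with them counted as DLTs.

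One sentence clarifying the G-CSF parenthesis for Cohorts 1 and 2 would be useful as a separate tidy-up.

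Cost: no new data, since doses, interruptions, relatedness and G-CSF use are already recorded. The downside is that cohorts may be paused for iDSMB review somewhat more often.

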### 6.5.2. Procedures for Cohort Review

Telephone conferences will be scheduled by the sponsor with study investigators to review cohort-specific data and overall safety data, to adjudicate individual high-grade AEs as potentially dose-limiting, and guide other major study decisions.

The decision to continue enrollment into each of the malignancy subtype cohorts will be based on the frequency of DLTs in the first 10 DLT-evaluable participants and review of ongoing

safety data. After the safety review is completed and the dose confirmation decision is made, the dose expansion period for that cohort will begin, and up to 10 additional participants will be enrolled (up to a total of 20 evaluable participants in each cohort across both study periods).

### **6.5.3. Dose-Limiting Toxicity Stopping Rules**

Participants in each of the disease-specific cohorts will be assessed for safety and tolerability using a continuous monitoring approach.

During the dose confirmation period, the occurrence of a DLT in  $\geq 2$  participants in a disease-specific cohort will trigger an iDSMB review. Enrollment will be halted in only that specific cohort until the iDSMB review is complete and the determination to continue enrollment (with or without protocol modifications) is made. The iDSMB review will result in nonbinding recommendations on further study conduct, that is, continue without modifications, continue with modifications, or terminate enrollment in the cohort. Please refer to the iDSMB charter for additional details.

Any DLT should be monitored until it resolves to baseline or appears to have stabilized for a minimum of 7 days. Participants should be seen as often as medically indicated to ensure appropriate management of the event.

## **6.6. Dose Modifications**

Treatment interruptions and modifications may occur for individual study participants.

### **6.6.1. Management of Dose-Limiting Toxicities or Other Urgent Situations**

Investigators may employ any measures or concomitant medications necessary to manage a DLT or other urgent situation after discussion with the sponsor (whenever possible).

### **6.6.2. Criteria and Procedures for Dose Interruptions and Adjustments of Study Drug**

Safety concerns should be discussed with the sponsor immediately upon occurrence or awareness of an event that may affect whether or not a participant should continue on study treatment.

Adverse events that have a clear alternative explanation or transient ( $\leq 72$  hours) abnormal laboratory values without associated clinically significant signs or symptoms may be exempt from dose reduction rules.

Because participants may enter the study with extensive pretreatment and/or severe bone marrow infiltration by the primary disease, dose modifications listed in [Table 8](#) are provided as general guidance. Individual decisions regarding dose reduction should be made using clinical judgment and in consultation with the sponsor's medical monitor, taking into account relatedness of the AE to the study drug(s) and the participant's underlying condition.

